9.3.2 Intent-to-Treat (ITT) Population

The ITT population includes all subjects who were enrolled and treated with the NanoKnife System. Any subject who has a NanoKnife probe inserted will be considered treated for the ITT population. The ITT population will serve as the primary analysis set for all safety and efficacy endpoints.

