10.6 Missing Data

Variables will be summarized for all eligible subjects with available data for the majority of endpoints/data (except for the endpoints/data detailed below). Missing data in the CRF will be detected by data management and monitored via edit checks and data analysis. Follow-up to collect missing data will be conducted as outlined in the Site Management Plan.

The following imputation methods will be applied:

- When calculating the proportion of subjects with a negative in-field biopsy, subjects with missing biopsy information post-ablation will be imputed as “positive”.
- Subjects with missing pre- or post-ablation prostate volume measurements will be imputed as having a zero change in volume. In accordance with the secondary endpoint related with “change in prostate volume”, this imputation will only be performed at Month 12 Visit.
- Missing PSA data will be imputed using last observation carried forward (LOCF).

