12.0 Statistical Methods

All analyses will use SAS® version 9.4 or higher. Table and listing outputs will be presented using PRA standard layouts, but sponsor guidance for numbering of statistical outputs will be used.

Unless specified otherwise, categorical variables will be summarized using counts and percentages. Percentages will be rounded to one decimal place, except 100% will be displayed without any decimal places and percentages will not be displayed for zero counts. Continuous variables will be summarized using the number of observations (n), mean, and standard deviation, median, minimum, 25th, and 75th percentiles, and maximum. The median, minimum, 25th, and 75th percentiles, and maximum values will be displayed to the same level of precision as the raw data, the mean and 95% confidence intervals (CI) to a further decimal place and the standard deviation to two additional decimal places to a maximum of four. The count of missing observations will be provided in all tables for information only.

The rate of negative in-field biopsy at 12 months will be calculated as the number of subjects with negative in-field biopsy on follow-up transperineal or transrectal biopsy at 12 months, divided by the total number of subjects still in the study at 12 months. Clopper-Pearson method ([Clopper and Pearson, 1934](#)) will be used to report 95% confidence interval (CI) as per requirement. The same approach will be followed for rate of negative in-field biopsy at 12 months as defined by the Delphi consensus criterion of absence of clinically significant disease (≤ 3 mm of Gleason ≤ 6 disease in any biopsy core is insignificant) ([Postema et al., 2016](#)).

For Kaplan-Meier method, the median time to event and associated 95% CI will be provided.

All statistical tests used generally are performed with a 2-sided alpha=5%. P-values will be rounded to 3 decimal places. P-values rounded to less than 0.001 will be reported as <0.001 in tables.

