12.1 Subject Disposition

The number and percentage of subjects screened and included in each analysis set will be presented, together with the number and percentage of subjects who withdrew from the study prematurely and a

breakdown of the corresponding reasons for withdrawal. A tabulation of the number and percentage of subjects enrolled at each center will be presented.

If a subject undergoes re-treatment, one re-treatment with IRE for the same lesion will allow the subject to continue in the study. However, if there is more than one re-treatment with IRE on the same lesion or at least one re-treatment with a type of treatment other than IRE, then the subject will exit the study (data until the moment of re-treatment will be used for analysis) and will only be followed up for safety purposes.

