12.7.1 Rate of Subjects with a Negative In-field Biopsy at 12 Months

The number and proportion of subjects obtaining a negative in-field biopsy at 12 months will be presented, along with the 95% confidence interval of the proportion. Clopper-Pearson method will be used to report 95% CI.

Subjects who are biopsied prior to 12 months (if there are positive findings on the 3-month mpMRI, if the subject is deemed to have biochemical progression, or if the treating physician deems there to be clinical suspicion) and have a positive in-field biopsy will be imputed as failures for the analysis of the primary efficacy endpoint.²

The rate of negative in-field biopsies will be compared to a performance goal of 0.52 using a one-sample non-inferiority test for proportions.

The null and alternative hypotheses for negative biopsy rate at 12 months are as follows:

H₀: NanoKnife System \leq (0.61 – margin of 0.09)

H₁: NanoKnife System $>$ (0.61 – margin of 0.09).

For subjects with a positive biopsy, Gleason total score will also be detailed.

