12.7.10 Sensitivity Analyses

All efficacy analysis will be repeated for the PP population. Additionally, a sensitivity analysis in the ITT population will be performed for the primary efficacy endpoint by only including subjects with biopsy data available at 12-months or who has a positive in-field biopsy prior to 12-months (i.e., without performing missing data imputation for subjects with missing biopsy information post-ablation).

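### SAP 12.0 divides the primary rate by the men still in the study at 12 months, so men the plan counts as failures can leave the denominator

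*Combined protocol and SAP*

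**What the plan says.** SAP 12.0 (Statistical Methods) defines the primary rate as the number of men with a negative in-field biopsy at 12 months, "divided by the total number of subjects still in the study at 12 months". It extends the same approach to the Delphi secondary rate. SAP 12.7.1 speaks of a number and proportion and names no denominator, so SAP 12.0 has the only explicit one.

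Other parts of the plan point to a different denominator:

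- SAP 9.3.2: "The ITT population will serve as the primary analysis set for all safety and efficacy endpoints". ITT means every man who had a probe inserted. SAP 12.7 presents efficacy for ITT, and the sample-size tables (protocol 6.2, SAP 8.1) name ITT as the primary population for this endpoint.
- SAP 10.6 and protocol 6.4: "subjects with missing biopsy information post-ablation will be imputed as" positive.
- SAP 12.7.1 and protocol 6.7: men biopsied early who "have a positive in-field biopsy will be imputed as failures for the analysis of the primary efficacy endpoint".
- SAP 12.7.10: the analysis without imputation is a sensitivity analysis, run "by only including subjects with biopsy data available at 12-months or who has a positive in-field biopsy prior to 12-months".

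SAP 12.1 decides who is still in the study. A man stays after a single repeat: "one re-treatment with IRE for the same lesion will allow the subject to continue in the study". After more than one IRE re-treatment of the same lesion, or "at least one re-treatment with a type of treatment other than IRE, then the subject will exit the study".

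SAP 6.1, which lists changes from the protocol, mentions no change of denominator.

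**The concern.** Imputing a missing biopsy as positive only works if the man stays in the denominator, and the same holds for an early in-field positive counted as a failure. Read literally, SAP 12.0 removes both kinds of men once they have left. Some leave because the treatment failed: a man with a confirmed early in-field positive who takes another therapy exits under SAP 12.1.

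The comparison with the performance goal also breaks. The goal is 0.61 − 0.09 = 0.52, and protocol 6.2 and SAP 8.1 say that the 0.61 was obtained with missing data imputed as positive. For a given number of negatives, a rate among remaining men is never lower than the ITT rate, and it is higher as soon as anyone leaves.

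The literal numerator has a related gap. A man with an early in-field positive and one IRE re-treatment stays in the study. If his 12-month biopsy is then negative, SAP 12.0 counts him as a success while SAP 12.7.1 counts him as a failure.

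The study is single-arm and unblinded (SAP 6.0), and the SAP gives no order of precedence between these sentences. The pivotal conclusion could depend on which one is programmed.

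**Working it through.** **Inputs from the documents.** Goal 0.52; assumed true rate 0.69; power 80%; efficacy N 51; safety N 100; drop-out 15%; enrolled N 118 (protocol 6.2, SAP 8.1). Clopper-Pearson 95% interval and a general two-sided 5% level (SAP 12.0).

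**Assumptions.** The plan states no alpha or sidedness for the primary test. I take success as a 95% Clopper-Pearson lower limit above 0.52, which is the exact test at one-sided 0.025, and repeat the key step at one-sided 0.05. Losses of 5% and 10%, and the 5 early-failure exits below, are mine to show a range. All 118 men are taken as treated.

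**1. The plan's own figures.** n = [z(1−α)·√(0.52×0.48) + z(0.80)·√(0.69×0.31)]² / (0.69−0.52)².

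- One-sided 0.05: (1.645×0.4996 + 0.842×0.4625)² / 0.0289 = 50.7, so 51. This reproduces the plan.
- One-sided 0.025: 64.8, so 65.
- Enrolled: 100/0.85 = 117.6, so 118. This reproduces the plan.

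**2. Negatives needed, ITT denominator.** 73/118 = 61.9%, lower limit 0.525, passes. 72/118 has lower limit 0.516 and fails.

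**3. Negatives needed, SAP 12.0 denominator.** A man who has left has no 12-month negative to contribute, so only the denominator shrinks.

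| Men out | Remaining | Fewest negatives to pass | SAP 12.0 rate | Same count over 118 (lower limit) |
|---|---|---|---|---|
| 0 | 118 | 73 | 61.9% | 61.9% (52.5%) |
| 6 | 112 | 70 | 62.5% | 59.3% (49.9%) |
| 12 | 106 | 66 | 62.3% | 55.9% (46.5%) |
| 18 | 100 | 63 | 63.0% | 53.4% (44.0%) |
| 18 + 5 early failures who exit | 95 | 60 | 63.2% | 50.8% (41.5%) |

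The counts that pass under SAP 12.0 and fail under ITT are 70–72 with 6 men out, 66–72 with 12 out and 63–72 with 18 out. In the last row a result passes although its ITT rate is below the goal itself.

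**4. Chance of a false success.** Let the true ITT rate, with missing as positive, be exactly 0.52 and let a fraction m leave. The rate among remaining men is then 0.52/(1−m), and the chance is P(X ≥ x*) for X ~ Bin(118(1−m), 0.52/(1−m)), where x* is the threshold from step 3.

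| m | Rate among remaining men | Fixed number remaining | Averaged over a binomial number remaining |
|---|---|---|---|
| 5% | 0.547 | 0.059 | 0.069 |
| 10% | 0.578 | 0.202 | 0.195 |
| 15% | 0.612 | 0.396 | 0.420 |

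Under the ITT rule, P(X ≥ 73 | 118, 0.52) = 0.0196.

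**5. If the test is one-sided 0.05.** The thresholds become 71/118 for ITT and 61/100 for SAP 12.0 with 18 out; 61/118 is 51.7%, again below the goal. False success is 0.046 under ITT, against 0.126, 0.291 and 0.541 with 5%, 10% and 15% out (averaged). The gap does not depend on the unstated alpha.

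**The case against.** The best defence is that the plan as a whole already settles the denominator, and SAP 12.0 is one stray general sentence. ITT is named repeatedly, protocol 6.5 includes every treated man in the analyses, both imputation rules assume it, and SAP 6.1 declares no departure. SAP 12.1 also says "then the subject will exit the study (data until the moment of re-treatment will be used for analysis"; an early positive biopsy comes before re-treatment, so that clause would keep the failure in the analysis. A careful programmer could well reach the ITT rate.

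This stands as a reading of intent, and it is why the point is a contradiction inside the SAP rather than a settled exclusion. It does not repair the sentence, which names this endpoint, states how the rate is calculated and has no competing formula.

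Several limits on the size also stand:

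- The 15% is a planning allowance for loss to follow-up, used to inflate the safety sample of 100. It is not a forecast, and with fewer exits the disputed band narrows as shown.
- Only some early failures are affected, because a man with one IRE re-treatment of the same lesion stays in.
- The false-success figures measure a change in what is estimated: with 15% gone, the rate among remaining men really is about 0.61.
- At the design rate of 0.69 the ITT rule passes with about 96% probability, so the choice of denominator matters most for middling results.
- SAP 12.0 is not identical to the no-imputation analysis in SAP 12.7.10. It keeps men still in the study without a biopsy, and it drops early in-field positives who exited, whom SAP 12.7.10 retains. The literal primary rate could therefore be more favourable than its own sensitivity analysis.

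**Conclusion.** The concern holds, and the sentence must be corrected. The denominator in SAP 12.0 contradicts the plan's ITT set, its missing-biopsy rule, its early-failure rule and the basis of the 0.52 goal. At the planned 15% loss it lowers the bar from 73 to 63 negatives and raises the chance of a false success from 2.0% to about 40–42% when the true ITT rate is 0.52. With 5% and 10% loss that chance is about 6–7% and 19–20%. These figures rest on 118 treated men, a 95% Clopper-Pearson lower limit above 0.52 as the success rule, and assumed loss fractions of which only the 15% is in the documents. The direction depends on none of these: for the same negatives, the SAP 12.0 rate exceeds the ITT rate whenever anyone leaves.

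**What to change.** Replace the sentence in SAP 12.0 with a definition such as:

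> *The primary rate is the count of ITT subjects whose 12-month in-field biopsy is negative and who had no earlier positive in-field biopsy, over all ITT subjects. A subject lacking a 12-month biopsy result counts as positive.*

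The second sentence settles a case that SAP 10.6 leaves open: a man with a negative early biopsy who then leaves before 12 months. That choice should be stated openly.

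Use the ITT denominator for the Delphi rate too, and add how an early in-field positive that is insignificant by the Delphi criterion is counted, since SAP 12.7.1 limits its early-failure rule to the primary endpoint. Keep the available-biopsy denominator only in SAP 12.7.10.

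The cost is one SAP sentence, the Delphi clarification and a table-shell denominator. No new data, visits or subjects are needed, and SAP 6.0 already foresees a final version before database lock. The reported rate will be less favourable when men leave the study.

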12.1 Subject Disposition

The number and percentage of subjects screened and included in each analysis set will be presented, together with the number and percentage of subjects who withdrew from the study prematurely and a

breakdown of the corresponding reasons for withdrawal. A tabulation of the number and percentage of subjects enrolled at each center will be presented.

If a subject undergoes re-treatment, one re-treatment with IRE for the same lesion will allow the subject to continue in the study. However, if there is more than one re-treatment with IRE on the same lesion or at least one re-treatment with a type of treatment other than IRE, then the subject will exit the study (data until the moment of re-treatment will be used for analysis) and will only be followed up for safety purposes.

12.2 Demographics

Demographics will include: age at informed consent, race, and ethnicity. Demographics will be reported for both ITT and PP subjects.

12.2.1 Medical History

Information regarding medical history will be presented, for both ITT and PP subjects. The number and percentage of subjects with each medical history term will be summarized by the Medical Dictionary for Regulatory Activities (MedDRA) system organ class (SOC) and preferred term. Medical history will be coded using MedDRA version 24.1 to assign a SOC and preferred term to each event.

12.3 Treatments

12.3.1 Prior Surgeries

Surgeries performed prior to NanoKnife will be reported for both ITT and PP subjects.

12.3.2 Concomitant Medications

Medications received concomitantly with study follow-up, during and after NanoKnife System treatment, categorized by medication group (ATC level 2) and subgroup (ATC level 4) according to WHODrug Sept2021), will be summarized. The number and percentage of subjects using each medication will be displayed together with the number and percentage of subjects using at least one medication within each medication group and subgroup. Concomitant medications will be reported for both ITT and PP subjects.

12.4 Prostate Cancer Diagnosis

Prostate Cancer Diagnosis information will be reported for both ITT and PP subjects. This information will comprise American Joint Committee on Cancer (AJCC) primary tumor stage, Gleason primary, secondary, and total sum score for the current diagnosis being treated.

12.5 Protocol Deviations

Per ICON Biotech Solutions processes, protocol deviations data will be entered into our system of record (Predictivv Study Operations [PSO]). The study team and the sponsor will conduct ongoing reviews of the deviation data from PSO and the resulting set of evaluable subjects throughout the study, adjusting the deviation criteria as seems appropriate. The evaluable subjects set must be finalized at the post-freeze data review meeting (or earlier), prior to database lock.

Based on the protocol deviations data entered into PSO, the protocol deviations thought to potentially impact the statistical analyses or subject safety will be listed and tabulated using incidence and percentages by deviation type for ITT subjects. Protocol deviations are defined in the protocol deviation guidance document. The last approved version of the protocol deviation guidance will be finalized before the database lock. The protocol deviance guidance will be used to exclude subjects from the PP population.

12.6 NanoKnife System Procedure

Details from the NanoKnife System procedure will be collected and presented in listings for both ITT and PP subjects. The details will comprise irreversible electroporation details, equipment used during NanoKnife procedure, physician assessment of procedure, and urinary catheterization. Device malfunctions will be summarized in a listing. Procedure duration (end time - start time), number of

electrodes, whether ultrasound/MRI fusion device was used during the procedure, urinary catheterization and its duration, physician assessment, and device malfunctions (i.e., were there any device malfunctions or error messages during the procedure?) will be also presented in a table for both ITT and PP subjects.

12.7 Efficacy Analyses

All efficacy analysis will be presented for the ITT population.

12.7.1 Rate of Subjects with a Negative In-field Biopsy at 12 Months

The number and proportion of subjects obtaining a negative in-field biopsy at 12 months will be presented, along with the 95% confidence interval of the proportion. Clopper-Pearson method will be used to report 95% CI.

Subjects who are biopsied prior to 12 months (if there are positive findings on the 3-month mpMRI, if the subject is deemed to have biochemical progression, or if the treating physician deems there to be clinical suspicion) and have a positive in-field biopsy will be imputed as failures for the analysis of the primary efficacy endpoint.²

The rate of negative in-field biopsies will be compared to a performance goal of 0.52 using a one-sample non-inferiority test for proportions.

The null and alternative hypotheses for negative biopsy rate at 12 months are as follows:

H₀: NanoKnife System \leq (0.61 – margin of 0.09)

H₁: NanoKnife System $>$ (0.61 – margin of 0.09).

For subjects with a positive biopsy, Gleason total score will also be detailed.

12.7.1.1 Subgroup analyses

Subgroup analyses will be performed for the primary efficacy endpoint as follows: i) Gleason score at screening: 3+4 vs 4+3; ii) Lesion size for the primary lesion (at visit 3): \leq 3 mm vs $>$ 3 mm; iii) Lesion location for the primary lesion (at visit 3): Base vs Apex; iv) Lesion location for the primary lesion (at visit 3): Anterior vs Posterior; v) PSA level at Screening: \leq 15 ng/mL vs $>$ 15 ng/mL.

12.7.2 Rate of Subjects with a Negative In-field Biopsy at 12 Months (Delphi Consensus)

The number and proportion of subjects obtaining a negative in-field biopsy at 12 months as defined by the Delphi consensus criterion of absence of clinically significant disease (\leq 3 mm in any biopsy core and Gleason Total Sum \leq 6 disease in any biopsy core is insignificant [[Postema et al., 2016](#)]) will be presented, along with the 95% confidence interval of the proportion. Clopper-Pearson method will be used to report 95% CI.

For subjects with a positive biopsy, Gleason total score will also be detailed.

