If the subject is re-biopsied, and there is a positive in-field core, this subject will be considered a failure for the primary efficacy endpoint (see Section 6.7). If the subject and the positive lesion still meet all of the inclusion criteria and none of the exclusion criteria⁴ (i.e., the lesion is an intermediate-risk lesion of Gleason 3+4 or 4+3 and all other criteria are met), the subject can be re-treated with the NanoKnife System and will continue to be followed up for the duration of the study for secondary efficacy endpoints and safety. If the subject and their treating physician decide on re-treatment with something other than the NanoKnife System, or if they no longer meet the inclusion/exclusion criteria for the study (i.e., they have a Gleason \geq 4+4 lesion and require whole-gland treatment), their post-re-treatment data will be excluded from the analysis.

Positive Early Out-of-Field Biopsy:

If the subject is re-biopsied, and there is a positive out-of-field core, this will not be considered a failure for the primary efficacy endpoint. If the subject and the new positive lesion still meet all of the inclusion criteria and none of the exclusion criteria⁵ (i.e., the new lesion is an intermediate-risk lesion of Gleason 3+4 or 4+3 and all other criteria are met), the subject can be re-treated for the new lesion with the NanoKnife System as part of the study. If the subject and their treating physician decide on re-treatment with something other than the NanoKnife System, or if they no longer meet the inclusion/exclusion criteria for the study (i.e., the new lesion is Gleason \geq 4+4 and the subject requires whole-gland treatment), they will exit the study though will continue to be followed for safety. These subjects who were re-treated with something other than the NanoKnife System for an out-of-field lesion prior to 12 months will have their post-re-treatment data excluded from the analysis.

Negative Early Biopsy:

If the subject is re-biopsied and there are no positive findings, they will continue in the study as planned, completing follow-up visits and the scheduled mpMRI and biopsy at 12 months.

If a subject is re-treated, regardless of the re-treatment selected, they should be followed up by the treating physician or their primary physician for routine urological care after the completion of the study.

Additional 'For Cause' Tests:

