6.9 Secondary Endpoints

Additional endpoints for statistical consideration will include the following:

- Rate of negative in-field biopsy at 12 months as defined by the Delphi consensus criterion of absence of clinically significant disease (≤ 3 mm of Gleason ≤ 6 disease in any biopsy core is insignificant)¹
- Assessment of urinary function by comparison of pre- and post-operative UCLA Expanded Prostate Cancer Index Composite (UCLA-EPIC) Urinary Domain² and International Prostate Symptom Scores (IPSS)³ and IPSS Quality of Life (IPSS-QoL) scores.
- Assessment of erectile function by comparison of pre- and post-operative 15-Item International Index of Erectile Function (IIEF-15)⁴ potency scores.
- Effectiveness of therapy by measurement of prostate-specific antigen (PSA) kinetics including time to PSA nadir.
- Assessment of changes in prostate volume by comparison of pre-treatment and 12-month prostate volume measured via mpMRI.
- Assessment of ablation effectiveness by evaluation of prostate tissue by mpMRI at 3 months post-treatment and at 12 months post-treatment.

- Assessment of need for secondary or adjuvant treatment following treatment with the NanoKnife System.
- Evaluation of subject reported pre- and post-operative Quality of Life (QoL) using the 5-dimension scale EuroQol (EQ-5D®).⁵

If a subject is re-treated with something other than the NanoKnife System during the study, secondary endpoint data collected during and after the re-treatment will not be included in the secondary endpoint analyses.

Negative in-field biopsy at 12 months as defined by Delphi consensus criteria: Negative in-field biopsy is defined to be the absence of clinically significant disease (≤ 3 mm of Gleason ≤ 6 disease in any biopsy core is insignificant).¹ Prostate cancer that is ≤ 3 mm Gleason 6 will be considered clinically insignificant cancer and will not be considered a positive biopsy for this endpoint.

UCLA-EPIC²: The Urinary domain score from the UCLA-EPIC (University of California Los Angeles Expanded Prostate Cancer Index Composite) Urinary questionnaire will be presented for each visit (i.e., 1, 3, 6, 9, and 12 month follow-up). In addition, the 6-month and 12-month change from baseline will also be tabulated. See **Appendix E – Subject Questionnaires – 1.1 UCLA-EPIC** section for more details on the questionnaire and scoring instructions.

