12.7.5 Effectiveness of Therapy by Measurement of PSA Kinetics

The mean PSA levels at each visit, the overall percent reduction in PSA levels (ng/mL) from screening to each visit (1, 3, 6, 9, and 12 month follow-up), and the proportion of subjects with a PSA reduction compared to screening at each visit will be presented. If a subject is re-treated during the study, all PSA values collected following the re-treatment will not be included in the analyses but will be included in the listings. Mean PSA nadir and post-nadir PSA values through 12 months post-treatment will be summarized. Kaplan-Meier analysis and summary statistics for time, including median time to event and associated 95% CI will be presented for PSA nadir. For this assessment, our baseline will be the screening measurements.

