12.7.7 Assessment of Ablation Effectiveness by Evaluation of Prostate Tissue by mpMRI

The number and proportion of subjects determined to have cancer-bearing prostate tissue lesions (i.e., modified prostate imaging reporting and data system [PI-RADS] 3 or higher lesion) on the 3 and 12-month mpMRI will be presented.

12.7.8 Assessment of Need for Secondary or Adjuvant Treatment Following Treatment with the NanoKnife System

The number and proportion of subjects undergoing secondary or adjuvant treatment during the study will be presented. Additional information regarding reason (positive unscheduled biopsy [in-field or out-of-field], clinical progression, biochemical progression, or other), location (index lesion or contralateral lesion), and type of re-retreatment (re-treatment with IRE, radical prostatectomy, high-intensity focused ultrasound [HIFU], cryotherapy, or other) will also be presented.

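### The Delphi biopsy rate has no early-failure rule, so a man re-ablated with NanoKnife after a significant in-field positive can count as a success

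*Combined protocol and SAP*

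**What the plan says.** **Primary endpoint.** SAP 12.7.1 states that subjects biopsied early who "have a positive in-field biopsy will be imputed as failures for the analysis of the primary efficacy endpoint". Protocol 4.6.16 agrees: after a positive early in-field core, "this subject will be considered a failure for the primary efficacy endpoint". Protocol 6.7 has the same rule with the same limit.

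**Re-treatment.** Under protocol 4.6.16 such a man "can be re-treated with the NanoKnife System and will continue to be followed up for the duration of the study for secondary efficacy endpoints"; his safety follow-up continues too. The condition is that subject and lesion still meet the eligibility criteria, explained as "the lesion is an intermediate-risk lesion of Gleason 3+4 or 4+3 and all other criteria are met". SAP 12.1 adds that one IRE re-treatment of the same lesion does not end participation; a second one, or any other therapy, does.

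**Exclusion of later data.** Protocol 6.9 covers one case only: "If a subject is re-treated with something other than the NanoKnife System during the study, secondary endpoint data collected during and after the re-treatment" are left out of the secondary analyses. NanoKnife re-treatment is not mentioned there.

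**Delphi endpoint.** SAP 12.7.2 gives "The number and proportion of subjects obtaining a negative in-field biopsy at 12 months as defined by the Delphi consensus criterion" with a Clopper-Pearson interval. Disease of at most 3 mm and Gleason 6 or below is disregarded. No early-biopsy or re-treatment rule follows, and protocol 6.9 has none for this endpoint.

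**PSA, for contrast.** In SAP 12.7.5, after any re-treatment, "all PSA values collected following the re-treatment will not be included in the analyses but will be included in the listings".

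**The concern.** The Delphi rate differs from the primary rate, on its face, only by tolerating clinically insignificant cancer. The gap between the two should therefore measure such cancer. If men rescued by a second ablation are primary failures but Delphi successes, the gap also contains the effect of re-treatment, and a reader of the two rates cannot separate the parts. The error runs in one direction only: it raises the Delphi rate.

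The path is a foreseen one. Protocol 4.6.16 calls for an early biopsy after a PI-RADS 3 or higher lesion on the 3-month mpMRI, after biochemical progression, or on clinical suspicion.

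**Working it through.** **1. One subject under the rules as written.** Take a man with Gleason 3+4 in-field on an early biopsy, one NanoKnife re-treatment, and a negative in-field biopsy at month 12.

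| Rule | Source | Result |
|---|---|---|
| Early in-field positive is a failure | SAP 12.7.1; protocol 4.6.16 and 6.7 | Primary: failure |
| Stays in for secondary efficacy | Protocol 4.6.16; SAP 12.1 | Delphi: still assessed |
| Later data dropped only after non-NanoKnife therapy | Protocol 6.9 | Delphi: month-12 biopsy is used |
| Missing biopsy counted as positive | SAP 10.6; protocol 6.4 | Not triggered; he has a biopsy |
| Month-12 result against the Delphi criterion | SAP 12.7.2 | Delphi: success |

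Re-treatment requires Gleason 3+4 or 4+3, above the Delphi limit of Gleason 6. So every man who qualifies for this path through an in-field lesion had Delphi-significant disease in the field after his first ablation.

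**2. Does other text close the gap?** A sentence in SAP 12.0 extends the approach for the primary rate to the Delphi rate. The paragraph it closes sets the numerator (negative at 12 months), the denominator (subjects still in the study then) and the Clopper-Pearson interval. The early-failure rule is not in it. SAP 12.7.10 mentions early in-field positives again, but for a sensitivity analysis of the primary endpoint.

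**3. Size.** The plan gives no expected Delphi rate, so there is no figure to reproduce for this endpoint. The enrolment figure does reproduce: 100 / (1 - 0.15) = 117.6, rounded up to 118.

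Let k be the number of men on this path who are negative at month 12. With the same denominator N under both handlings:

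inflation = k / N, so one man adds 1/118 = 0.85 points (1/100 = 1.0 point if N = 100).

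For illustration, borrow the plan's 69% (stated for the primary rate) as the Delphi rate with an early-failure rule: 0.69 x 118 = 81.4, taken as 81.

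| k | Delphi rate without the rule | 95% Clopper-Pearson | Inflation (points) |
|---|---|---|---|
| 0 | 81/118 = 68.6% | 59.5-76.9 | 0 |
| 3 | 84/118 = 71.2% | 62.1-79.2 | 2.5 |
| 6 | 87/118 = 73.7% | 64.8-81.4 | 5.1 |
| 9 | 90/118 = 76.3% | 67.6-83.6 | 7.6 |

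The documents do not give k. As an assumption, multiply the share re-ablated by the share of those negative at month 12:

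| Re-ablated | 50% then negative | 90% then negative |
|---|---|---|
| 2% | 1.0 | 1.8 |
| 5% | 2.5 | 4.5 |
| 10% | 5.0 | 9.0 |

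**4. How far can the range go?** Under the plan's 69%, 0.31 x 118 = 36.6 subjects fail the primary endpoint. If the planned 15% drop-out is all counted as positive, 0.15 x 118 = 17.7 of these are missing, leaving 36.6 - 17.7 = 18.9 men with a positive biopsy. Ten per cent re-ablated is 11.8 men, or 11.8/18.9 = 62% of them. The top of the range is already demanding.

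**The case against.** **Repeat ablation may be the intended estimand.** Protocol 4.6.16 deliberately keeps NanoKnife re-treated men for secondary efficacy, and SAP 12.1 permits one repeat. That is a coherent quantity, control after up to two ablations, but neither document says the Delphi rate measures it. The endpoint shares its name and time point with a primary rate that treats these men the other way.

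**The re-treated men are visible.** SAP 12.7.8 tabulates re-treatment by reason (including an in-field unscheduled biopsy), location and type, and SAP 12.7.1 and 12.7.2 give Gleason scores for positive biopsies. This stands. It lets a careful reader bound k, but does not correct the reported rate or its interval.

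**The SAP 12.0 sentence could be read as carrying the rule over.** An analyst might read it so, which is a further reason to settle the matter in writing. The text does not say it.

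**PSA is not a precedent for counting failures.** Correct. SAP 12.7.5 drops values after re-treatment and imputes nothing. It shows only that re-treatment was handled for one secondary endpoint and not for this one; it does not show what the authors intended for biopsy.

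**The mpMRI endpoint.** A reader might infer that SAP 12.7.7 likewise turns a re-ablated man into an ablation success. The documents do not support that. The section counts subjects "determined to have cancer-bearing prostate tissue lesions" at 3 and at 12 months and defines neither success nor failure, and a lesion seen at 3 months stays in the 3-month proportion. The month-12 figure does mix re-treated and once-treated men, and does not separate in-field from out-of-field lesions. That is a presentation matter.

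**Conclusion.** The point holds for the Delphi endpoint. Followed as written, the rules count a failed first ablation rescued by a second NanoKnife treatment as a Delphi success and raise the rate by k/N: 0.85 points per man at N = 118, and about 1 to 9 points if 2-10% are re-ablated and 50-90% of those are then negative. Both shares are assumptions. N may be below 118, given the denominator in SAP 12.0.

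Two stronger readings should be resisted. Inflation of 12 points or more would need, for example, 18 of 118 men re-ablated and 80% of them negative (14.4/118 = 12.2 points). Against about 18.9 biopsy-positive men, nearly all would have to be found early, qualify again and choose NanoKnife. Nor is the trial's main conclusion at risk: the primary endpoint has its own rule, and protocol 6.2 says the study is not powered for claims on secondary endpoints. The change should be made because the rate will be reported with a confidence interval beside the primary result.

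**What to change.** Add to SAP 12.7.2 and protocol 6.9: *A subject with in-field disease above the Delphi threshold on any biopsy before month 12 is a failure for this endpoint and stays in the denominator, regardless of re-treatment or later results.* Report the rate that uses the month-12 result after NanoKnife re-treatment as a sensitivity analysis. The rule must use the Delphi threshold, because an early core with insignificant Gleason 6 is positive for the primary endpoint but not for this one.

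In SAP 12.7.7, do not impute lesions that were not seen. Show the 12-month mpMRI proportion with and without subjects re-treated in-field. Split in-field from out-of-field lesions only if the CRF records location; the CRF is not in the documents, so this needs checking.

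The cost is a few lines before database lock. For NanoKnife re-treated men the early biopsy grade settles the classification, since it is a condition of re-treatment. An early Gleason 6 core also needs its cancer length, so confirm that this is recorded for unscheduled biopsies. No clinical rule changes. The reported Delphi rate falls by k/N, and by somewhat more if men who left for another therapy would otherwise have dropped out of the denominator.
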